### 4.3 Description of Study Procedures

#### 4.3.1 Efficacy

RECIST v1.1 (Eisenhauer et al, 2009; see [Appendix E](#)) will be used to assess subject response to treatment and allow calculation of PFS, ORR, and DoR, which will be performed according to the schedules in Section 4.2. Post-radiation changes which affect lesion sizes may occur and there may be high levels of necrosis/fibrosis with little or no active tumor in recently irradiated lesions. However, accepting these limitations in this patient population with prior curative radiation treatment, the prior irradiated lesions may be considered measurable and selected as target lesions providing they fulfill the other criteria for measurability. All images will be collected and stored for possible future central re-analysis. Additional disease assessments may be performed as clinically indicated.

Additionally, disease progression in the absence of clinical deterioration requires confirmation. The confirmatory scan should occur preferably at the next scheduled visit and no earlier than 4 weeks after the initial assessment of PD. Administration of study drug(s) may continue between the initial assessment of progression and confirmation for progression. Subjects with rapid tumor progression or with symptomatic progression that requires urgent medical intervention (eg, central nervous system metastasis, respiratory failure due to tumor

compression, spinal cord compression) will not be eligible to continue to receive study drug(s) neither will require a confirmatory scan.

CCI

CCI

- If progression is not confirmed, then the subject should continue study drug(s) and on treatment assessments.
- If repeat scans confirm progression, then the date of the initial scan should be declared as the date of progression.

Tumor assessments may include the following evaluations: cross-sectional imaging using computed tomography (CT) or magnetic resonance imaging (MRI) scan of the chest, abdomen, and brain.

- MRI (preferred) or CT scans of the brain will be performed at screening for all subjects
- CT or MRI scan of the chest and abdomen will be performed at screening and with each disease assessment for all subjects.

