- PFS, defined as the time from randomization until the first documentation of disease progression according to RECIST v1.1 or death due to any cause, whichever occurs first, regardless of whether the subject receives subsequent anticancer therapy prior to progression. Subjects who are alive progression free at the time of DCO will be censored on the date of their last evaluable tumor assessment. PFS-12 will be estimated using the Kaplan-Meier method.

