#### **3.4.2.1 Best Overall Response**

Best overall response (BOR) will be based on all post-baseline disease assessments that occur prior to disease progression, and/or prior to the initiation of subsequent anticancer treatment. BOR will be summarized with the number and percentage of subjects for the following categories: complete response (CR); partial response (PR); stable disease (SD); progressive disease (PD); and non-evaluable (NE). At least 7 weeks (8 weeks minus 1 week to allow for the protocol-defined disease assessment window) from randomization of IP must elapse without a subsequently radiological disease progression to assign a best overall response of SD.

Confirmation of CR and PR is required and must occur at least 4 weeks after initial documentation of CR or PR. If CR is pending confirmation and is designated at an assessment followed by 1 or more NE assessments, and/or PR assessments such that 1) the Target Lesion Response is CR and the Non-Target Lesion Response is NE, or 2) the Target Lesion Response is PR due solely to an increase in one or more lymph nodes to a size  $\geq 10$  mm and the Non-Target Lesion Response is either CR or NE, CR may be confirmed thereafter. Similarly, if a PR is pending confirmation and is designated at an assessment followed by 1 or more NE and/or SD assessments, PR may be confirmed thereafter.

In general, subjects not classifiable under the RECIST v1.1 response categories due to insufficient data or early death will be classified as NE for BOR but will be counted in the denominator of all response rate calculations. This generalization includes if a subject has missing lesion data at baseline. In this scenario, the subject will be classified as NE for BOR.

If a subject is missing lesion data at a disease assessment and yet PD criteria is met despite the missing data, the subject will be classified as PD.

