**Table 3.4.1      Summary of Censoring Guidelines for PFS**

Situation	Date of PD/Death or Censoring	PFS Outcome
Documented Progressive Disease (PD) or death	Date of earliest sign of PD or death, whichever comes first	Event (unless the censoring rule specified below)
Death or PD immediately after $\geq 2$ consecutive missed or non-evaluable disease assessments as per the protocol specified assessment schedule	Date of last progression-free disease assessment prior to missed or non-evaluable assessments, or randomization, whichever occurred last	Censored
No PD or death at time of analysis or lost to follow-up	Date of last evaluable progression-free disease assessment	Censored
No tumor assessment at baseline and no evidence of PD at first post-baseline disease assessment OR No tumor assessment post-first dose, and no death prior to second scheduled post-baseline disease assessment	Date of randomization	Censored

PD = progressive disease; PFS = progression-free survival.

Subjects having missing lesion data at baseline or no disease assessments post-first dose of IP will have PFS censored at the date of randomization unless the subject dies prior to the second scheduled post-baseline disease assessment in which case the death date will qualify as a PFS event.

If a subject has two or more consecutive completely missed or non-evaluable assessments followed immediately by death or an assessment showing radiologic disease progression, then the subject will be censored for PFS. PFS will be censored at the date of randomization or the last progression-free disease assessment prior to the missed or non-evaluable assessments, whichever occurred last.

If a subject has two or more consecutively missed or non-evaluable assessments followed by an assessment showing no radiologic disease progression, then the assumption will be that the subject did not progress during the missed or non-evaluable assessments.

The length of gap (in number of days) to determine two or more consecutive assessments is defined as the following:

- 126 days during the first 12 months (A 8-week disease assessment interval plus a 7-day window for each assessment).

- 182 days from month 12 to month 24 (A 12-week disease assessment interval plus a 7-day window for each assessment).
- 422 days after month 24 (A 6-month disease assessment interval plus a 4-week window for each assessment).

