### 7.1.3 Disease Assessment Overall Response per RECIST v1.1

Investigator visit disease response will be programmatically derived on the data collection instrument using RECIST v1.1 criteria based upon target lesion response, non-target lesion response, and new lesion data. Missing values in any of target lesion response, non-target lesion response, and new lesion data will result in the disease response not being derived.

Possible values include:

- CR – Complete Response

- PR – Partial Response
- SD – Stable Disease
- PD – Progressive Disease
- NE – Non-evaluable

Target Lesion Response	Non-Target Lesion Response	New Lesion	Derived RECIST Disease Response
CR	CR or NA	No	CR
CR	Non-CR/Non-PD or NE	No (or NE)	PR
PR	CR or Non-CR/Non-PD or NE or NA	No (or NE)	PR
SD	CR or Non-CR/Non-PD or NE or NA	No (or NE)	SD
PD	Any	Any	PD
Any	PD	Any	PD
Any	Any	Yes	PD
NE	CR or Non-CR/Non-PD or NE or NA	No	NE
NA	CR	No	CR
NA	Non-CR/Non-PD	No	SD (Non-CR/Non-PD) a
NA	NE or NA	No (or NE)	NE
NA	CR or Non-CR/Non-PD	NE	SD (Non-CR/Non-PD) a

a Per RECIST v1.1, “SD (Non-CR/Non-PD)” is preferred over “SD” for non-target disease since SD is increasingly used as endpoint for assessment of efficacy in some trials so to assign this category when no lesions can be measured is not advised.

*(Note: “(or NE)” values under New Lesion will only be included in confirmation of progression or confirmation of new lesions are required per protocol. The last 4 rows may be eliminated from any study that requires identification of at least one measurable lesion at Baseline. One may choose to allow such cells to remain if an independent central review is included in the trial.)*

If a subject has a missing tumor measurement at some assessment(s) for 1 or more target lesions and criteria for PD are not otherwise met, an overall response of NE will be assigned for the assessment(s).

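### Protocol 4.3.1 asks for a scan to confirm progression, but Protocol 4.8.3 and the SAP count the first PD; where PD is not confirmed, PFS (and sometimes ORR, DCR or DoR) depends on which rule applies

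*Protocol*

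**What the plan says.** Protocol 4.3.1 opens by saying that RECIST v1.1 assessments feed the calculation of PFS, ORR and DoR. It then states that "disease progression in the absence of clinical deterioration requires confirmation", by a scan at least 4 weeks after the first PD. Two bullets follow:

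- "If repeat scans confirm progression, then the date of the initial scan should be declared as the date of progression"
- "If progression is not confirmed, then the subject should continue study drug(s) and on treatment assessments"

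Subjects with rapid or symptomatic progression are exempt; for them the text says "neither will require a confirmatory scan". Redacted blocks stand directly before the two bullets.

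The protocol's statistical section reads differently. Section 4.8.3 defines PFS as "the time from randomization until the first documentation of disease progression according to RECIST v1.1 or death due to any cause", and DoR ends at the same kind of event. Appendix F requires confirmation of CR and PR only.

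The SAP follows 4.8.3. Its PFS event date in Table 3.4.1 is "Date of earliest sign of PD or death, whichever comes first". Section 7.1.5 takes the first date on which any objective test shows PD. Under 3.4.2.1, best overall response "will be based on all post-baseline disease assessments that occur prior to disease progression". Outside 7.1.3, the SAP mentions confirmed progression only in 2.2, as a reason for stopping treatment.

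In the SAP 7.1.3 response table, the PR and SD rows accept a new-lesion entry of No (or NE). The note beneath says that these NE "values under New Lesion will only be included in confirmation of progression or confirmation of new lesions are required per protocol". Protocol Table F1 gives PR or SD only where new lesions are recorded as No.

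**The concern.** The first bullet of 4.3.1 does more than guide treatment. It assigns a progression date, and does so on condition of confirmation. Nothing in the visible text says how a PD scan counts for the endpoints when the repeat scan does not bear it out. One reading sets that scan aside; 4.8.3 and the SAP make it the PFS event and the end of the best-response window.

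The situation is foreseeable here. Inclusion criterion 6 requires a measurable, previously irradiated lesion, and 4.3.1 itself warns that post-radiation changes affect lesion size. The trial is open-label, the endpoints rest on investigator measurements (SAP 3.4.2), and the investigator judges eligibility for a confirming scan (Protocol 4.1.6). With two progression rules on paper, a choice between them could be made after the data are seen. No visible analysis shows whether the conclusion depends on that choice.

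The NE entries in SAP 7.1.3 add to the doubt. By the table's own note they belong only in a study that requires confirmation, yet no SAP endpoint uses confirmed progression. Their practical effect is that a visit at which new lesions could not be assessed may still count as PR or SD.

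**Working it through.** **The plan's own figure.** Protocol Table 9 gives, for 30/60 against 18/60, a difference of 20% (1%, 38%). An exact unconditional interval ordered on the raw difference reproduces it: 20.0% (1.3%, 37.7%). It also reproduces the other three rows: 10% (-8.7, 28.2), 15% (-3.7, 32.9) and 25% (6.4, 42.3).

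**Size of one subject.** 1/60 = 1.7 percentage points. With one experimental responder fewer, the difference is 29/60 - 18/60 = 11/60 = 18.3%, with interval (-0.4%, 36.1%) by the method that reproduces Table 9. A score-ordered exact interval gives (0.6%, 35.3%), so whether the lower limit crosses zero depends on the method. This shows only how close that row lies to the boundary.

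**Where the two rules part.** The histories below are assumed, with scans every 8 weeks as in Protocol Table 5. Rule A counts the first PD. Rule B counts PD only if the next scan confirms it or there is clinical deterioration, dated to the first PD scan. Entries are A / B.

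| History (scan week) | PFS | OR | DC at 16 weeks | DoR |
|---|---|---|---|---|
| 1. PR 8, 16; PD 24; PR 32, 40; PD 48, 56 | event 24 / event 48 | yes / yes | yes / yes | 16 / 40 weeks |
| 2. PD 8; SD 16; PR 24, 32, 40 | event 8 / censored 40 | no / yes | no / yes | none / 16 weeks, censored |
| 3. SD 8, 16; PD 24; SD 32, 40 | event 24 / censored 40 | no / no | yes / yes | none / none |
| 4. PD 8; SD 16, 24, 32 | event 8 / censored 32 | no / no | no / yes | none / none |
| 5. SD 8; PD 16, 24 (confirmed) | event 16 / event 16 | no / no | no / no | none / none |
| 6. SD 8; PD 16 with deterioration, no second scan | event 16 / event 16 | no / no | no / no | none / none |
| 7. SD 8, 16; PR 24; PD 32; PR 40, 48 | event 32 / censored 48 | no / yes | yes / yes | none / 8 weeks, censored |

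Five histories (1, 2, 3, 4, 7) have a PD that the repeat scan does not confirm. PFS differs in all five, DoR in three, OR in two and DC in two. These counts describe the examples and are not expected frequencies. The pattern is:

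- PFS differs whenever a required repeat scan fails to confirm PD.
- OR differs only if the confirmed response needs scans taken after that PD.
- DC differs only if the PD came before disease control was established.
- DoR differs only for subjects who are responders under at least one rule.

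**Illustration of scale.** The documents give no rate of unconfirmed PD. Assuming 2% to 10% of an arm of 60, 1.2 to 6 subjects would be affected. All would have a different PFS. A shift of 2 to 10 points in one arm's DCR or ORR is a ceiling, reached only if every such subject's status changed. The difference between arms moves only by the net of the two arms' shifts, which could be nil.

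**Interim rule.** The No-Go cutoffs in Protocol Table 10 are whole counts. With 18 control subjects in disease control, 14 in the experimental arm is a No-Go and 15 is not. History 4 moves such a count by one.

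**SAP 7.1.3 against Table F1.** Target PR, non-target non-CR/non-PD and new lesions NE give PR under the SAP. Table F1 has no PR row for that combination and no row at all for new lesions NE. Simply deleting the NE entries would leave these visits without a derived response.

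**The case against.** The strongest reply is that the endpoint rule is already settled. Protocol 4.8.3 makes RECIST v1.1 the primary basis and uses first documentation of PD, Appendix F confirms only CR and PR, and the SAP agrees throughout. Section 4.3.1 sits among study procedures, and the discontinuation criteria in 4.1.6 cite it, so it can be read mainly as a rule on continuing treatment. Its bullet on unconfirmed PD speaks only of continuing drug and assessments. The redacted text before the bullets may limit their scope, and the SAP version history records that iRECIST is not reported in the CSR.

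Much of this stands. A reader might infer that the SAP contradicts the protocol as a whole; it does not, since 4.3.1 stands against the protocol's own 4.8.3 as well as the SAP. A reader might also infer that 4.3.1 makes an unconfirmed PD vanish from best response and PFS. Rule B above is a reading of that section, not its text. What remains is that the dating sentence is worded as an endpoint rule, and nothing visible says it does not apply to the endpoints.

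On SAP 7.1.3, the note may be template wording and does not decide when PD counts. The table's difference from Table F1 remains.

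**Conclusion.** The inconsistency is real and worth correcting. It lies between Protocol 4.3.1 on one side and Protocol 4.8.3, Appendix F and the SAP on the other.

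A reader might conclude that ORR, DCR, DoR and PFS all differ for every subject with unconfirmed PD. The documents do not support that. Of the seven histories only the second changes all four endpoints, and subjects exempt from a confirming scan are not affected. Nor is there ground for saying that the comparison between arms is biased: no rate of unconfirmed PD is given, and nothing shows that it would differ by arm.

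The supported size is 1.7 points per affected subject in an arm of 60 for ORR or DCR, where that subject's status changes, and a changed PFS time or event status for each subject whose PD is not confirmed. This rests on reading 4.3.1 as setting unconfirmed PD aside, and on the redacted text not saying otherwise. The mismatch between SAP 7.1.3 and Table F1 does not depend on that reading; how many visits it touches is unknown.

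**What to change.** 1. State in Protocol 4.3.1 that its confirmation and dating text does not alter the endpoints, and that first documented RECIST v1.1 PD, as in 4.8.3, governs BOR, ORR, DCR, DoR and PFS.
2. In SAP 7.1.3, remove the NE new-lesion entries from the PR and SD rows. Add a row that maps target CR, PR or SD with new lesions NE, and no PD otherwise, to overall NE.
3. Add one sensitivity analysis of ORR and PFS, by arm, in which a PD scan followed by a non-PD scan at least 4 weeks later is disregarded. A PD with no later scan stays a PD.

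The cost is wording in both documents and one extra analysis. The scans are already collected, because Protocol 4.2.2 keeps subjects with unconfirmed PD who are eligible for a confirmation scan in scheduled follow-up. The downside of item 2 is that ORR may be slightly lower, since some visits now scored PR would become NE. No change to treatment-continuation rules is proposed.

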### **Computed Tomography Scan**

- CT (contrast preferred) scans of the chest and abdomen should be performed with contiguous cuts in slice thickness of 5 mm or less. Spiral CT should be performed using a 5-mm contiguous reconstruction algorithm. The same imaging device should be used for serial evaluations.

### **Magnetic Resonance Imaging Scan**

- MRI scan of the chest and abdomen is acceptable for measurement of lesions provided that the same anatomical plane is used for serial assessments.
- In case of MRI, measurements will be preferably performed in the axial (transverse) plane on contrast-enhanced T1-weighted images. However, there are no specific sequence recommendations.

4.3.1.1

CCI

CCI

## CCI

### 4.3.1.2 Disease assessment by PET

Local changes and the presence of distal metastasis will be assessed by positron emission tomography (PET). The methods for assessing metabolic update by PET are summarized below ([Plathow et al, 2011](#)).

- PET requires measurement of the metabolically active lesions and background area. The FDG-distribution is rated visually and quantified as standardized uptake values (SUV).
- Any focal tracer uptake in lesions with SUV peak at least 1.5-fold greater than liver SUV mean is considered metastatic in absence of any alternative explanation. If liver is abnormal, primary tumor lesion should have uptake at least 2.0-fold greater than SUV mean of blood pool in descending thoracic aorta.
- For each lesion suspicious for malignancy in PET/CT, the site-based localization (lymph nodes, lung, liver, adrenal gland, brain, other viscera, and bone) is recorded.
- These parameters can be recorded as exploratory data on up to 5 measurable target lesions, typically the 5 hottest lesions, which are typically the largest, and no more than 2 per organ. Tumor size of these lesions can be determined per RECIST v1.1.
- Additional SUV measures including SUV mean, SUV peak or volumetric information may be measured to assess suspicious lesions.

### 4.3.2 Medical History, Physical Examination, Electrocardiogram, and Vital Signs

#### Medical History

Medical history will be collected at screening. Based on findings from medical history, ongoing current conditions will be given a baseline grade according to the procedure for AEs. Increases in severity of pre-existing conditions during the study will be considered AEs, with resolution occurring when the grade returns to the pre-study grade or below.

#### Physical Examinations

Physical examinations will be performed according to the schedules in Section [4.2](#). A complete physical examination will be performed at screening and should include assessments of the head, eyes, ears, nose, and throat, respiratory, cardiovascular, gastrointestinal, musculoskeletal, neurological, psychiatric, dermatological, hematologic/lymphatic, endocrine systems, and weight to 0.1 kg; and height (at screening only). Abbreviated symptom-directed physical examinations will be conducted at subsequent visits post dosing.

#### Vital Signs

Vital signs (blood pressure and pulse rate) will be measured according to the schedules in Section 4.2. For all vital sign measurements, subjects should rest for at least 10 minutes in a supine or semi-recumbent position, and all vital sign measurements should be taken prior to any blood draws or other procedures whenever possible.

## ECG

Resting 12-lead ECGs will be recorded at screening and as clinically indicated throughout the study as presented in Section 4.2. ECGs should be obtained after the subject has been in a supine position for 5 minutes and recorded while the subject remains in that position.

In cases when the first ECG shows clinically significant abnormalities, including a QTcF value  $\geq 470$  ms, 2 additional 12-lead ECGs should be obtained over a brief period (eg, 30 minutes) to confirm the finding based on the average of all 3 manually overread ECGs by a medically qualified delegate.

### 4.3.3 Clinical Laboratory Tests

A Laboratory Manual will be provided to the sites that specifies the procedures for collection, processing, storage, and shipment of samples, as well as laboratory contact information, specific to this clinical research study.

Clinical laboratory safety tests, including serum pregnancy tests, will be performed in a licensed clinical laboratory. Urine pregnancy tests may be performed at the site using a licensed test (dipstick). Abnormal laboratory results should be repeated using a serum pregnancy test as soon as possible (preferably within 24 to 48 hours).

The following clinical laboratory tests will be performed (see Section 4.2 for the schedule of tests):

#### Serum Chemistry

- Albumin
- Amylase
- ALP
- ALT
- AST
- Bicarbonate
- Blood urea nitrogen / urea
- Calcium
- Chloride
- Creatinine
- Gamma-glutamyl transferase
- Glucose
- Lactate dehydrogenase
- Lipase
- Magnesium
- Potassium
- Sodium
- Total bilirubin (TBL; direct bilirubin should be obtained if TBL is  $>$  ULN)
- Total protein
- C-reactive protein

ULN = upper limit of normal

**Note:** Tests for AST, ALT, ALP, and TBL must be conducted concurrently and assessed concurrently.

## Hematology

- Absolute lymphocyte count
- Absolute neutrophil count
- Hemoglobin
- Platelet count
- White blood cell count

## Urinalysis

- Blood
- Protein

## Pregnancy Test (females of childbearing potential only)

- Urine hCG
- Serum  $\beta$ -hCG (or required if a urine hCG is equivocal or positive)

$\beta$ -hCG = beta-human chorionic gonadotropin; hCG = human chorionic gonadotropin.

